#### 14.1.3.3. FT3, FT4 and TSH serum levels

TSH level results that are below the limit of quantitation (BLQ) will be treated as value for descriptive statistics but presented as ' $<$  value', in listings. The BLQ levels will be confirmed by Apitope or the IQVIA Central Laboratory prior to database lock.

The following summaries will be provided for the Thyroid function tests serum level data:

- Descriptive statistics (observed, change from baseline and percentage change from baseline) will be presented for each parameter at baseline and at each post-baseline visit for each analysis population as applicable.
- Shift from baseline to each scheduled protocol post-baseline visit for FT3, FT4 and TSH serum levels categorised according to normal reference range as low, normal and high, as well as a subcategory for markedly high. The high and markedly high categories are not mutually exclusive, thus the markedly high results will be included in the high category count. For the shift the percentage (%) of subjects in each category calculated relative to the total number of subjects in the relevant analysis population with assessments available at baseline and the relevant post-baseline visit per parameter.
- Incidence of markedly high results per time point of FT3 ( $>20$  pmol/L) and FT4 ( $>45$  pmol/L) for the ITT population.

Only data up to the time point of dosing with anti-thyroid drugs will be included in summary tables and figures of efficacy for subjects in the anti-thyroid drug population.

The following figures will be presented for the ITT population:

- Line graph of geometric means  $\pm$  95% CI limits (geometric) for FT3 and FT4.
- Line graph of change from baseline and percentage change from baseline means  $\pm$  SD for FT3 and FT4.
- Line graph of individual FT3 and FT4 results over time. Horizontal dotted lines will indicate the normal range lower and upper limits for each parameter.

---

Document: ATX\_GD\_59 Final 1.0 SAP 28FEB2018.docx  
Author: [name]

Version Number: Final 1.0  
Version Date: 28FEB2018

Template No: CS\_TP\_BS016 Revision 4  
Effective Date: 01Apr2016

Reference: CS\_WI\_BS005

- Scatter plots of each of change from baseline and percentage change from baseline versus baseline levels for FT3 and FT4 at Week 18, 22 and 30 will be presented with different colours/symbols on the same graph.
- Histograms of geometric means by timepoint, with a horizontal bar to indicate the normal range and vertical dotted line on the SD1 bar, to denote start of treatment, on the Week 10 bar to denote end of titration period and on the Week 22 bar to denote end of full treatment period for observed results for FT3 and FT4.

FT3, FT4 and TSH serum levels will be presented in a by-subject listings for the Study population including observed results, change from baseline, percentage change from baseline and fold change from baseline (see section 14.2.2.1). Results outside the normal range and above the markedly abnormal range (trigger values) for administration of anti-thyroid drug administration (FT3 > 20 pmol/L and/or FT4 > 45 pmol/L on 2 consecutive scheduled/unscheduled visits) will be flagged (i.e. worst case flag will be presented). Assessments post administration of anti-thyroid drugs will also be flagged.

Note that individual subjects with FT3, FT4 and TSH results outside of normal range and with clinical markedly abnormal laboratory results will also be listed with safety laboratory listings.

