6. Subject requires treatments prohibited by the exclusion criteria or the protocol.
7. Subject demonstrates a robust and increasing positive response in the anti-drug anti-body assay accompanied by clinical signs of an adverse immune response to either peptide in ATX-GD-59. These may be unexplained chills, fever or flu like symptoms following treatment with ATX-GD-59.
8. Subject becomes pregnant.

Management of thyrotoxicosis during the study

- Symptomatic patients may be treated with propranolol (up to 160mg per day) adjusted to control tachycardia or other symptoms. If alternative beta-adrenergic receptor blockade is required, this must be agreed with the study medical monitor.
- If there is a contraindication to using a beta blocker (e.g., asthma) then rate limiting calcium channel blockers (e.g. Diltiazem MR 120 to 240mg daily) may be used instead. This must also be agreed with the study medical monitor.

Administration of Anti Thyroid Drug's during the study is indicated in the following instances:

- A subject has trigger levels of free T3 (>20pM) and/or free T4 (>45pM) on 2 consecutive scheduled or unscheduled visits.
- Continued weight loss >5kg from baseline (Study Day 1).
- Persistent tachycardia >120bpm.
- Significant cardiac event that would require urgent treatment of thyrotoxicosis.
- If the investigator or treating physician considers that it is appropriate to administer anti-thyroid drugs at any point during the study.

Duration of treatment:

The trial consists of a screening visit, a dosing period of 18 weeks, an efficacy assessment after 4 weeks (post final dose) and a follow-up period of 8 weeks.

Dose and mode of administration:

ATX-GD-59 is a lyophilised equimolar mixture of two peptides reconstituted at the clinic to provide one of two different concentrations, depending on dose, for injection prior to intradermal injection.

Dose Strengths: 4mg/ml and 0.5mg/ml total peptide content when reconstituted in water for injection and 0.9% saline respectively.

Safety monitoring and analysis:

Subjects will be observed in the clinic for at least two hours after administration of the study drug and vital signs will be recorded at 15 minute intervals for the first hour and 30 minute intervals for the second hour. If the subject is well (in the opinion of the Investigator), they will then be allowed to leave the clinic. A contact card with an emergency telephone number will be provided to each subject.

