## 4.3. CHANGES TO ANALYSIS FROM PROTOCOL

### 4.3.1. POPULATIONS

The Per-protocol (PP) population requirements stated in the protocol (see section 20.4.2) included subjects required to receive the full treatment regimen (i.e., all doses received and at least 80% of protocol-specified total study drug volume injected for the entire treatment period). Compliance with respect to study drug volume ( $\mu$ L) injected will be replaced by compliance with respect to total study drug dose ( $\mu$ g) injected. Since the eCRF records changes from planned dose injected, not changes from planned dose volume injected and the direct calculation between study drug dose and volume, this change was implemented for consistency for reporting of study drug dosing data. Further the PP population will only be summarised separately, if it represents at least 50% of the total Intention-to-treat (ITT) population and is different from the ITT population by at least one subject.

The definition of the anti-thyroid drug population in the protocol (see section 20.4.3) is defined as the PP population plus those who had received anti-thyroid drugs during the ATX-GD-59 dosing and follow-up period to Week 22. Following a discussion with Apitope, the definition for the anti-thyroid drug population for analysis was updated to any ITT subject taking anti-thyroid drugs at any time post first dose of ATX-GD-59 up to and including the Week 22 visit. Further, this population will only be summarised separately, if it represents at least 50% of the total ITT population and is different from the ITT population by at least one subject.

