#### 5.4.3. ANTI-THYROID DRUG POPULATION

A third analysis population, the anti-thyroid drug population, is defined as any ITT subject taking anti-thyroid drugs at any time post first dose of ATX-GD-59 to the Week 22 visit.

Efficacy parameters will be summarised for the anti-thyroid drug population provided that it differs from the ITT population by at least one subject and is at least 50% of the ITT population.

All data will be listed for subjects in the anti-thyroid drug population, however, only data up to the time point of dosing with anti-thyroid drugs will be included in summary tables of efficacy (TSHR antibodies and thyroid function tests for subjects in the anti-thyroid drug population). Additionally, visits post administration of anti-thyroid drugs in these subjects will be flagged in all by-visit listings of efficacy and safety data except diary card recordings of injection site reactions, and listings of exploratory efficacy parameter data (B set).

---

Document: ATX\_GD\_59 Final 1.0 SAP 28FEB2018.docx  
Author: [name]

Version Number: Final 1.0  
Version Date: 28FEB2018

Template No: CS\_TP\_BS016 Revision 4  
Effective Date: 01Apr2016

Reference: CS\_WI\_BS005

Copyright © 2009, 2010, 2012, 2016 Quintiles Transnational Corp. All rights reserved.  
The contents of this document are confidential and proprietary to Quintiles Transnational Corp. Unauthorized use, disclosure or reproduction is strictly prohibited.

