#### 4.1.4. ANTI-THYROID DRUG POPULATION

The anti-thyroid drug population is defined as any ITT subject taking anti-thyroid drugs at any time post first dose of ATX-GD-59 up to the Week 22 visit.

Exclusion criterion from the anti-thyroid drug population:

- All subjects excluded from the ITT population.
- All subjects not taking anti-thyroid drugs at any time post first dose of ATX-GD-59 to the Week 22 visit.

**CRITERION [7]:** Did not Receive Anti-thyroid Drugs prior to Week 22.

FIXED CATEGORY: Concomitant Medications.

STATUS: Yes/No

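### FT3/FT4 summaries exclude post-rescue values only for anti-thyroid drug starts up to Week 22, although Week 30 is summarised, and no efficacy table shows how many subjects had been rescued by each visit

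*SAP*

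**What the plan says.** The exclusion appears twice in the SAP. Section 14.1.3.3 gives it for FT3, FT4 and TSH: "Only data up to the time point of dosing with anti-thyroid drugs will be included in summary tables and figures of efficacy". The same sentence limits its scope to "summary tables and figures of efficacy for subjects in the anti-thyroid drug population". Section 5.4.3 gives it for tables alone: "only data up to the time point of dosing with anti-thyroid drugs will be included in summary tables of efficacy".

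Membership of that population ends at Week 22. SAP 4.3.1 defines it as "any ITT subject taking anti-thyroid drugs at any time post first dose of ATX-GD-59 up to and including the Week 22 visit". In Appendix 4, section 4.1.4, the label of criterion [7] is "Did not Receive Anti-thyroid Drugs prior to Week 22", which treats the boundary day differently.

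The efficacy summaries run later than that. SAP 4.3.8 extends by-visit summaries to Week 30, where the protocol had stopped at Week 22, and 14.1.3.3 plans FT3/FT4 scatter plots at Weeks 18, 22 and 30. Missing efficacy data are not imputed (7.3, 14.1.2), and shift-table percentages use only subjects with a value at that visit (14.1.3.3). The per-protocol population removes only subjects given ATD before the Week 22 visit (5.4.2).

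The protocol synopsis lists several indications for ATD. One is: "A subject has trigger levels of free T3 (>20pM) and/or free T4 (>45pM) on 2 consecutive scheduled or unscheduled visits". SAP 14.1.3.3 uses the same two limits to define markedly high.

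**The concern.** There are two linked problems.

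First, the same event is handled in two ways according to its date. After an ATD start by Week 22, later values are cut. After a start between Weeks 22 and 30, the Week 30 value is kept, although it was measured on ATD, and it can be read as a result of the study drug.

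Second, when ATD starts because FT3 or FT4 has stayed above the trigger, the cut removes a subject because of high values of the variable being summarised. Later means and markedly-high percentages then describe only subjects not yet rescued.

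An effect on FT3/FT4 is a secondary objective of a single-arm proof-of-principle study, so no control group would reveal either effect. At stake is how the Week 18, 22 and 30 changes are read. No error rate is involved.

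**Working it through.** **1. Week 30, from the text.** Take an ITT subject who starts ATD at Week 24.
- 5.4.3: not in the ATD population, so the cut does not apply.
- 4.3.8: Week 30 is summarised, so the on-ATD value enters the ITT tables.
- 5.4.2: not excluded from per-protocol on this ground, so the value enters those tables too if the subject otherwise qualifies.
- Flags: 5.4.3 promises that "visits post administration of anti-thyroid drugs in these subjects will be flagged in all by-visit listings of efficacy and safety data", where these subjects are the ATD population. 14.1.3.3 has no such limit: "Assessments post administration of anti-thyroid drugs will also be flagged". A flag in a listing changes no table.

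**2. Can the ATD-population summary show the earlier starters?** It is produced only if that population is at least 50% of ITT (5.4.3). With about 15 treated subjects (protocol synopsis), 7/15 = 47% fails and 8/15 = 53% passes. With 1 to 7 starters there is no such summary, and any that is produced is itself cut at ATD start.

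**3. Direction and size for earlier starters.** The plan has no figure to reproduce. It gives no ATD rate, SD, baseline distribution or ATD effect. Assumptions: 15 subjects, baseline FT3 uniform on 7 to 15 pmol/L, no study-drug effect, ATD only after FT3 >20 at two consecutive scheduled visits, with the triggering value kept; 20,000 runs. The FT4 limb and unscheduled visits are not modelled.

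Drift model (log FT3 follows a random walk):

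| 22-week log SD | 0.3 | 0.4 | 0.5 | 0.6 |
|---|---|---|---|---|
| Share removed before Week 22 | 0.029 | 0.068 | 0.109 | 0.153 |
| Removed, of 15 | 0.4 | 1.0 | 1.6 | 2.3 |
| Week 22 fold change, observed (true 1.00) | 0.986 | 0.962 | 0.927 | 0.884 |
| SE of mean log fold | 0.075 | 0.099 | 0.123 | 0.148 |
| Bias in SE = abs(ln fold)/SE | 0.2 | 0.4 | 0.6 | 0.8 |
| Markedly high, Week 22, of available | 2.4% | 4.2% | 5.8% | 7.1% |
| Markedly high, nobody removed | 4.4% | 8.7% | 12.8% | 16.6% |

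Noise model (each visit scatters independently about the subject's baseline; log SD 0.2/0.3/0.4): the mean is 1.00 throughout, and markedly high reads 1.1/4.2/7.9% against 1.1/4.4/8.6% with nobody removed.

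**4. The other reading of the scope.** If the cut covers only the ATD-population tables, on-ATD values stay in the ITT means. If ATD is assumed to multiply FT3 by 0.5, the Week 22 fold change under drift reads 0.98/0.96/0.93/0.90.

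**5. Week 30 under each rule (drift model).** At least one of 15 subjects completes the trigger with the Week 22 result in 9/16/21/24% of runs.
- SAP rule, ATD factor 0.7: 0.984/0.958/0.921/0.876.
- SAP rule, ATD factor 0.5: 0.982/0.954/0.915/0.870.
- One rule through Week 30: 0.983/0.954/0.913/0.865.

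If k of 12 subjects kept at Week 30 are on ATD for any reason, the geometric mean is multiplied by f^(k/12). For k = 1/3/6 this is 0.97/0.91/0.84 with f = 0.7 and 0.94/0.84/0.71 with f = 0.5. These values of k are illustrations; the documents give no rate.

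**The case against.** The strongest reply is that the study is descriptive, its primary objective is safety, and the cut at rescue is openly specified. The protocol places its efficacy assessment four weeks after the last dose, at Week 22, so an ATD window that closes there is not arbitrary. Rescue can also be seen elsewhere: in population counts and withdrawal reasons (SAP 9), medication tables (12), flagged listings, and n as a default statistic (6.6). Trigger values at scheduled visits still count in the markedly-high and shift tables.

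Much of this stands, and it lowers the severity. But n shows that a table shrank, not why, and the individual line graphs are efficacy figures subject to the same cut. None of these outputs puts the number already rescued beside the visit mean. By adding Week 30, the SAP itself opened the gap after Week 22.

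Four stronger readings are tempting and not supported.
- That the ITT tables certainly drop these values. This is the natural reading, but the SAP does not say so outright.
- That the Week 22 limit is what makes Week 30 look favourable, or that one rule would cure it. In step 5 the single rule leaves the mean no less selected.
- That the bias is always favourable. It is absent from the mean under pure noise, and its direction is not shown for ATD started on other grounds or for TBII and TSAb.
- That a failure endpoint is therefore required. SAP 4.3.4 declined a responder endpoint with reasons, and a composite of ever markedly high or ATD started would reach 10/30/49% on visit noise alone.

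The boundary-day wording, the absence of the rule from 14.2.2 and the unstated denominator for markedly-high incidence are mostly missing detail. Section 5.4.3 probably reaches the 14.2.2 tables, though it does not mention figures and 14.2.2.2 plans scatter plots.

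**Conclusion.** The point holds. On the text alone, on-ATD Week 30 values after a late start remain in the ITT summaries, and in the per-protocol summaries for otherwise eligible subjects. For earlier starters, either reading of the rule can make late FT3/FT4 results look favourable: by dropping subjects because their values were high, or by keeping their values on ATD if ATD lowers hormone levels.

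The size cannot be known from the documents. Under assumed drift, the Week 22 mean moves by 1% to 12%, less than one standard error, and the markedly-high share reads roughly half of what it would be with nobody removed. Under pure visit noise, the mean does not move and the share barely does. The modelled Week 30 difference between the two rules is small, so the case for one rule is consistency and not reading ATD effects as study-drug effects. Severity is minor to moderate.

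**What to change.** 1. State that the exclusion follows each ITT subject's own ATD start date, not membership of the ATD population, and applies to every start through Week 30. State that it covers all ITT and per-protocol FT3/FT4 tables and figures, including those in 14.2.2, and how a start on the Week 22 visit day is treated. This makes the rule consistent and takes on-ATD values out, but does not remove the selection.
2. Beside each FT3/FT4 by-visit table, print the cumulative n (%) of subjects who have started ATD, on the full ITT denominator. Read the Week 18, 22 and 30 changes with that row. State the denominator of the markedly-high incidence at the same time.

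Keep the observed-case tables. The composite of ever markedly high or ATD started, and a worst-rank summary labelled as an unfavourable bound, are optional.

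The cost is SAP wording and one count row per table, with no new data. The downside is a smaller n at Week 30 and a possibly less favourable picture.

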1 SUMMARY/SYNOPSIS

Title of Study:	Safety and proof of principle study of ATX-GD-59 in male and female subjects with Graves' disease not currently treated with anti-thyroid therapy: An Open label study, with an upward titration over five dose levels administered by Intradermal injection.
Countries:	United Kingdom
Phase of development:	Phase I
Study Objectives:	

PRIMARY
 
 • To evaluate whether ATX-GD-59 administration every two weeks by intradermal injection is safe and well tolerated in male and female subjects with Graves' disease, not currently treated with anti-thyroid therapy. 	

SECONDARY
 
 • To assess the effects of ATX-GD-59 on TSHR antibody levels. • To assess the ratio of stimulatory vs inhibitory TSHR antibodies. • To assess the effect of ATX-GD-59 on free T3, free T4 and TSH serum levels. 	

EXPLORATORY
 
 • To assess the effects of ATX-GD-59 on TSHR induced Peripheral Blood Mononuclear Cell (PBMC) T cell activity. • To assess the effects of ATX-GD-59 on the T cell cytokine signature. • To assess the effects of ATX-GD-59 IL-10 pathway and associated genes (mRNA). 	
Methodology:	

This will be an open label, ascending dose evaluation of the safety, tolerability and efficacy of ATX-GD-59 in approximately 12 evaluable subjects with Graves' disease who are HLA-DRB1*15, HLA-DRB1*03 and/or HLA-DRB1*04 positive and not currently treated with anti-thyroid therapy.
 
The first four subjects will be recruited sequentially with a minimum of 48 hours between the first dose of each subject. Individual subject safety data will be reviewed by the Investigator and the Sponsor or Sponsor's representative after the first dose of ATX-GD-59. Dosing of the remaining subjects will only commence once the first subject has received the second dose and there are no safety concerns identified.
 
There will be an upward titration over five dose levels (injection(s) of 25, 50, 100, 400 and 800 µg) of ATX-GD-59 followed by injection(s) of 800 µg injected on five further occasions. All doses are based on the total peptide.
 
All doses will be administered by intradermal injection at intervals of 14 +/- 3 days.
 
An estimated 33 subjects will be screened, with approximately 15 subjects receiving at least one dose of ATX-GD-59.
	

Number of Subjects: Approximately 12 subjects to complete dosing and attend the Week 22 visit.
	

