Inclusion criteria

1. A diagnosis of Graves' disease as assessed by a physician from clinical and laboratory findings and not receiving anti-thyroid therapy.
2. Quantifiable levels of TSHR antibodies.
3. Raised levels of free T3 and/or free T4 (not exceeding 15 pmol/L and 35 pmol/L respectively) including undetectable levels of thyroid stimulating hormone.
4. HLA-DRB1*15, HLA DRB1*03 and or HLA DRB1*04 positive.
5. Age 18 – 65 years inclusive at the time of informed consent.
6. The subject must be willing and able to give written informed consent and must be willing to comply with protocol assessments/procedures.
7. Male subjects must be sterile (biologically or surgically) or commit to the use of a reliable method of birth control for the duration of the study until at least 90 days after the last dose of ATX-GD-59.
8. Female subjects of child bearing potential must:
 - neither be pregnant nor breast-feeding, nor attempting to conceive, and
 - use a highly effective method of contraception as defined below, throughout the entire duration of the study and for at least 90 days after the last dose of ATX-GD-59.

A serum pregnancy test will be performed at the screening visit in women of child bearing potential. Thereafter urine pregnancy tests will be performed. A positive result will exclude the woman from the study immediately.

A highly effective method of contraception is defined as those which result in a low failure rate when used consistently and correctly such as implants, injectable, combined oral contraceptives, some Intrauterine Devices (IUDs), unless post-menopausal or surgically sterilized. Barrier forms of contraception are considered appropriate when used in combination with one of the above methods.

Exclusion criteria

1. Subjects who are pregnant or breastfeeding and/or subjects in the post-partum period.
2. A known history of, or hypersensitivity reactions that in the opinion of the investigator would exclude the subjects' participation in the study.
3. Treatment with any Anti-Thyroid Drugs e.g. carbimazole within the previous 3 months prior to Study Day 1.
4. Previous treatment with radioiodine or (partial or complete) thyroidectomy.
5. Signs of moderate or severe orbitopathy including optic nerve compression requiring steroids and/or a clinical activity score >3.
6. Large and compressive goitres causing localised symptoms such as difficulty swallowing or breathing.

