## 4. STUDY DESIGN

### 4.1. GENERAL DESCRIPTION

This is a phase I, first in human, open-label within subject dose-escalating study to evaluate the safety and efficacy of ATX-GD-59 in approximately 12 evaluable subjects with Graves' disease who are HLA-DRB1\*15, HLA-DRB1\*03 and/or HLA-DRB1\*04 positive and not currently treated with anti-thyroid therapy.

There will be an upward titration over five dose levels (injection(s) of 25, 50, 100, 400 and 800 µg) of ATX-GD-59, followed by a further five injections of the highest dose (expected to be 800 µg total peptide). All doses are based on the total peptide.

No control group will be utilized in this study and all subjects will receive the same dose-escalation schedule of ATX-GD-59.

All doses will be administered by intradermal injection to the anterior abdominal wall or thigh at intervals of 14 +/- 3 days.

---

Document: ATX\_GD\_59 Final 1.0 SAP 28FEB2018.docx  
Author: [name]

Version Number: Final 1.0  
Version Date: 28FEB2018

Template No: CS\_TP\_BS016 Revision 4  
Effective Date: 01Apr2016

Reference: CS\_WI\_BS005

Copyright © 2009, 2010, 2012, 2016 Quintiles Transnational Corp. All rights reserved.  
The contents of this document are confidential and proprietary to Quintiles Transnational Corp. Unauthorized use, disclosure or reproduction is strictly prohibited.

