### 6.2. BASELINE

Unless otherwise specified, baseline is defined as the last available assessment (scheduled or unscheduled) prior to the first administration of study drug. In the case where the last non-missing measurement prior to first administration of study drug and the reference start date coincide, that measurement will be considered baseline.

Baseline and at each scheduled post-baseline visit as well as separately for multiple assessments within a visit, change from pre-dose to each post-dose assessment will also be evaluated.

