### **6.7.2. PERCENTAGE CHANGE FROM BASELINE**

For FT3, FT4 and TSH, percentage (%) change from baseline will be calculated as:

- $(\text{Post-dose value} - \text{Baseline value}) / \text{Baseline value} * 100$

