## **7. STATISTICAL CONSIDERATIONS**

### **7.1. ADJUSTMENTS FOR COVARIATES AND FACTORS TO BE INCLUDED IN ANALYSES**

Not applicable, as no adjustment for covariates and factors will be done for this study.

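### The FT3/FT4 scatter plots set change from baseline against the same baseline value, so a downward slope is expected without any drug effect if spread stays similar, and there is no control group to gauge it

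*SAP*

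**What the plan says.** The figure list for the ITT population in SAP section 14.1.3.3 includes "Scatter plots of each of change from baseline and percentage change from baseline versus baseline levels for FT3 and FT4". Three visits share each panel: the plots "for FT3 and FT4 at Week 18, 22 and 30 will be presented with different colours/symbols on the same graph".

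SAP section 6.2 says that "baseline is defined as the last available assessment (scheduled or unscheduled) prior to the first administration of study drug", so each subject has one baseline value, normally the Study Day 1 pre-dose sample. SAP section 6.7.2 covers the relative measure: "For FT3, FT4 and TSH, percentage (%) change from baseline will be calculated as" the post-dose value minus baseline, divided by baseline, times 100.

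The design gives no external reference. SAP section 4.1 states: "No control group will be utilized in this study and all subjects will receive the same dose-escalation schedule of ATX-GD-59". SAP section 7.1 adds that "no adjustment for covariates and factors will be done for this study". The Protocol synopsis aims for "Approximately 12 subjects to complete dosing and attend the Week 22 visit". Inclusion criterion 3 selects on the plotted variables: "Raised levels of free T3 and/or free T4 (not exceeding 15 pmol/L and 35 pmol/L respectively".

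The SAP attaches no fitted line, coefficient or p-value to these plots, and section 6.6 calls all presentations descriptive. The documents supplied contain no caution about regression to the mean or shared terms for this figure.

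**The concern.** Any transient fluctuation or assay error in the single baseline value enters the two axes with opposite signs. A subject whose Study Day 1 FT3 happens to be high sits to the right and, other things equal, shows a larger fall later. A subject who happens to be low sits to the left and shows a smaller fall or a rise. The cloud then tilts downward although nobody's underlying level has changed, which looks like greater improvement at higher starting levels.

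Putting three visits on one graph does not provide three independent checks. All three changes for a subject use the same baseline, so an error in it moves all three points the same way.

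Among the outputs specified for FT3 and FT4, this figure is the one that relates change directly to starting level. Without a control arm, nothing in the trial shows how much of a slope would have appeared untreated.

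**Working it through.** **Inputs.** From the documents: the axes and visits (SAP 14.1.3.3), the single baseline (6.2), the percentage formula (6.7.2), no control group (4.1), about 12 completers and entry caps of 15 and 35 pmol/L (Protocol synopsis). Assumed, because the documents do not give them: rho, the correlation between baseline and follow-up; k, the ratio of follow-up SD to baseline SD; and, for the simulations, normal values with stated means and SDs. The plan gives no figure of its own to reproduce.

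**Closed form with no drug effect.** Write B for baseline and F for follow-up, in units of the baseline SD.

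- Cov(F - B, B) = k·rho - 1, which is also the slope.
- Var(F - B) = 1 + k² - 2k·rho.
- r = (k·rho - 1) / sqrt(1 + k² - 2k·rho).

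With k = 1 this reduces to r = -sqrt((1 - rho)/2). For rho = 0.7, sqrt(0.3/2) = 0.387, so r = -0.39.

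**Equal spread (k = 1).** The last three columns come from 6,000 simulated null trials per row at n = 12, with assumed mean 10 and SD 2.5 pmol/L. The p-value column only indicates how convincing the cloud would look; the SAP plans no such test.

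| rho | slope | expected r | absolute change: r below 0 | absolute change: r below 0 and p < 0.05 | percentage change: mean r |
|---|---|---|---|---|---|
| 0.3 | -0.7 | -0.59 | 98% | 57% | -0.58 |
| 0.5 | -0.5 | -0.50 | 96% | 41% | -0.50 |
| 0.7 | -0.3 | -0.39 | 91% | 25% | -0.39 |
| 0.8 | -0.2 | -0.32 | 85% | 17% | -0.31 |
| 0.9 | -0.1 | -0.22 | 77% | 10% | -0.22 |

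**With entry limits applied at Screening.** For absolute change at n = 12 and rho from 0.3 to 0.9, mean r runs from -0.58 to -0.26 for FT3 (cap 15; assumed lower limit 6.8, mean 10, SD 2.5) and from -0.59 to -0.31 for FT4 (cap 35; assumed lower limit 22, mean 27, SD 6). The caps do not remove the pattern.

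**Unequal spread.** The numerator k·rho - 1 is zero at k = 1/rho and positive beyond it.

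- rho = 0.8: k = 1.25 gives r = 0.00 and k = 1.5 gives +0.22.
- rho = 0.7: k = 1.25 gives -0.14 and k = 1.5 gives +0.05.
- rho = 0.5: k = 1.25 gives -0.33 and k = 2 gives 0.00.

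**Alternative x-axes under the same null.**

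- *Screening value.* Let each measurement be a stable level with variance rho plus an error with variance 1 - rho, and let the Screening and Study Day 1 errors have correlation a. Then Cov(F - B, Screening) = -a(1 - rho), so r = -a·sqrt((1 - rho)/2). With a = 0, r = 0, and simulation at n = 12 gave about 0.00 with a negative sign in about half of trials. With a = 0.3, 0.5 and 0.7, r is -0.15, -0.25 and -0.35 at rho 0.5, and -0.12, -0.19 and -0.27 at rho 0.7. The fraction of the artefact that remains equals a. This is for absolute change.
- *Mean of baseline and follow-up.* r = (k² - 1) / sqrt((1 + k²)² - 4k²·rho²). This is 0 at k = 1 for every rho, but +0.35 at k = 1.25 and rho = 0.8.

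**The case against.** The best reply is that this is one untested figure in a descriptive study of about 12 evaluable subjects. The SAP defines no responder endpoint (4.3.4) and plans no subgroup analyses (7.5). Its planned correlations relate FT3 and FT4 to TBII and TSAb (14.2.2.2), never to their own baseline. Individual trajectories and by-subject listings, including Screening thyroid tests (section 10), let a careful reader see the fluctuation. The output shells, which were not available, might already carry a caution. All of this stands, and it limits the consequence. It does not change the expected shape of the figure as specified.

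Three stronger readings are tempting, and the documents do not support them.

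- A reader might infer that the plots must show higher-baseline subjects improving most, whatever the drug does. That is an expectation under similar spread, not a certainty. Entry is capped at 15 and 35 pmol/L, while the trigger levels for anti-thyroid drugs are above 20 and 45, so follow-up spread could exceed baseline spread. Efficacy figures omit data after anti-thyroid drugs start, which could limit that widening or add to the pattern; neither effect was quantified.
- A reader might infer that these plots will decide who is studied next. Nothing in either document gives them that role, and the SAP does not claim that higher baseline predicts improvement.
- A reader might infer that moving Screening to the x-axis cures the problem. It does so only if fluctuation four weeks apart is independent, which disease activity need not be.

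**Conclusion.** The point holds as an expectation. With no drug effect and similar spread at the two times, the planned plots should slope downward for any rho below 1. The correlation is about -0.50, -0.39 and -0.32 at rho 0.5, 0.7 and 0.8, and percentage change behaves much the same. The size rests on an assumed rho and on k near 1; the association disappears at k = 1/rho and reverses beyond it. Without a control group, an observed slope cannot be divided into artefact and real baseline-dependent effect. The consequence is confined to the reading of one secondary, descriptive figure. It is worth correcting because the correction costs almost nothing.

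**What to change.** In SAP section 14.1.3.3, add to the planned plots, or substitute for them, one or both of the following for FT3 and FT4:

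1. Change from the Study Day 1 baseline against the Screening (Week -4) value. Mark or omit any subject whose baseline is itself the Screening value.
2. Change from baseline against the mean of the baseline and follow-up values.

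If the planned plot is kept, footnote it to say that a downward slope is expected even without a drug effect, because baseline is part of both axes.

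The cost is a changed or added figure specification; both pre-dose samples are already scheduled. The limits should be stated with the figures. The Screening axis is narrowed by the eligibility limits, and a fraction of the artefact equal to the Screening to Study Day 1 error correlation remains. The mean-based plot is centred on zero under no effect only when baseline and follow-up spreads are equal. Neither option deals with the omission of data after anti-thyroid drugs start.
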